	d) Location of Ovaprene™ in relation to the cervix as determined by clinical exam; relationship of position to PCT results, safety, and acceptability.	Ovaprene™ safety cycle and Ovaprene™ PCT cycles

Version: 06.00 (FINAL) Date: June 13, 2019

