#### 3.6 Efficacy Analysis

All efficacy analyses will be done for the Ovaprene with at Least One PCT Cycle population, and may be repeated for Treated with Caya population when necessary. The primary efficacy analysis will be the changes in PCT results due to Ovaprene® device use, and consists of the following 6 endpoints:

a) The proportion (and 95% exact binomial confidence interval ) of subjects with an average of fewer than 5 progressively motile sperm per HPF in cervical mucus, after sex at ovulation in the absence of the device. This needs to use the "Average number of progressively motile sperm" (SAS variable name MUAVPMS) in Cervical Mucus CRF, and count the number of subjects with MUAVPMS < 5.0 at the Visit 3 (BP2); then divided by the total number of subjects with PMS measurements at this visit, and finally converted to a percentage (multiplied by 100). In the data listing of PMS data, the data that occur in a cycle after a dislodgement in the e-diary, and clinician noted dislodgement, will be flagged.

This primary efficacy analysis will be repeated by subgroups for:

- (1) Had vaginal ring use before enrolling in the study vs. Never had
- (2) Had vaginal delivery vs. caesarean birth
- (3) BMI ≥30 (Obese) vs. <30 at Baseline
- (4) Study site EVMS vs. Non-EVMS study sites
- (5) Device position at the time PCT: Over cervical os, Not over cervical os on anterior vaginal wall, Not over cervical os and not on anterior vaginal wall

- (6) Dislodgments (dislodgement reported in cycle before the PCT visit vs. no dislodgements reported in cycle before PCT).
- b) The sample size, mean, median, standard deviation, and interquartile range (IQR, i.e., 25th and 75th percentiles), for the average number (across 9 HPFs) of progressively motile sperm per HPF in cervical mucus, across all treated subjects, in the absence of the device. This is to summarize the same field (MUAVPMS) in the above Bullet a) as a continuous variable at Visit BP2.
- c) The proportion of subjects (and 95% exact binomial confidence interval) with an average of fewer than 5 progressively motile sperm per HPF in cervical mucus, in the presence of the Ovaprene® device. This is similar to that in Bullet a), but will be done at Visit OP3A, and at Visit OP3B, by sub-setting the CRF data at VISIT\_ID = 14, and at VISIT\_ID = 19, respectively.

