| 14.1.9-En           | Summary of Pregnancy History for All Enrolled Population  | All Enrolled      |
| 14.1.9-Ca           | Summary of Pregnancy History for Caya Population  | Caya              |
| 14.1.9              | Summary of Pregnancy History  | Ovaprene          |
| 14.1.10-Ca          | Number and Percent of Subjects with Prior Medication Use by Drug Class and Generic Name for Caya Population | Caya              |
| 14.1.10             | Number and Percent of Subjects with Prior Medication Use by Drug Class and Generic Name                     | Ovaprene          |

| Table Number    | Table Title   | Population                    |
|-----------------|---|--------------------------------------|
| 14.1.11-Ca      | Number and Percent of Subjects with Concomitant Medication Use by Drug Class and Generic Name for Caya Population for Caya Population                                   | Caya                                 |
| 14.1.11         | Number and Percent of Subjects with Concomitant Medication Use by Drug Class and Generic Name   | Ovaprene                             |
| 14.2.1.1        | Number and Percent of Subjects with an Average of Fewer Than 5 Progressively Motile Sperm per HPF in Cervical Mucus   | Ovaprene with at Least One PCT Cycle |
| 14.2.1.1-Ca     | Number and Percent of Subjects who Used Caya and Had an Average of Fewer Than 5 Progressively Motile Sperm per HPF in Cervical Mucus for Caya Population                | Caya                                 |
| 14.2.1.1-R      | Number and Percent of Subjects with an Average of Fewer Than 5 Progressively Motile Sperm per HPF in Cervical Mucus by Prior Vaginal Ring Use and Not Before Enrollment | Ovaprene with at Least One PCT Cycle |
| 14.2.1.1-BMI    | Number and Percent of Subjects with an Average of Fewer Than 5 Progressively Motile Sperm per HPF in Cervical Mucus by Subjects BMI at Least 30 vs Less Than 30         | Ovaprene with at Least One PCT Cycle |
| 14.2.1.1-E-NE   | Number and Percent of Subjects with an Average of Fewer Than 5 Progressively Motile Sperm per HPF in Cervical Mucus by EVMS and Non-EVMS Sites                          | Ovaprene with at Least One PCT Cycle |
| 14.2.1.1-Dev    | Number and Percent of Subjects with an Average of Fewer Than 5 Progressively Motile Sperm per HPF in Cervical Mucus by Device Position at the Time PCT                  | Ovaprene with at Least One PCT Cycle |

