| 14.2.1.1-Dis    | Number and Percent of Subjects with an Average of Fewer Than 5 Progressively Motile Sperm per HPF in Cervical Mucus by Subjects Had Ring Dislodgement or Not            | Ovaprene with at Least One PCT Cycle |
| 14.2.1.2        | Average Number (across 9 HPFs) of Progressively Motile Sperm per HPF in Cervical Mucus and Change from Baseline Cycle to Ovaprene PCT Cycles                            | Ovaprene with at Least One PCT Cycle |
| 14.2.1.3        | Number and Percent of Ovaprene Cycles with Fewer Than 5 PMS per HPF in Cervical Mucus   | Ovaprene with at Least One PCT Cycle |
| 14.2.1.4        | Number and Percent of Subjects with Fewer Than 5 PMS per HPF in Cervical Mucus  | Ovaprene with at Least One PCT Cycle |
| 14.2.2.1-E      | Summary of the Levels of Ferrous Gluconate in CVF at Study Site EVMS  | Ovaprene with at Least One PCT Cycle |
| 14.2.2.1-E-5PMS | Summary of the Levels of Ferrous Gluconate in CVF at Study Site EVMS for Subjects with Fewer Than 5 PMS per HPF in the Cervical Mucus after Sex                         | Ovaprene with at Least One PCT Cycle |
| 14.2.2.1-NE     | Summary of the Levels of Ferrous Gluconate in CVF at Non-EVMS Sites   | Ovaprene with at Least One PCT Cycle |

| Table Number         | Table Title  | Population                    |
|----------------------|--|--------------------------------------|
| 14.2.2.1-NE-
5PMS | Summary of the Levels of Ferrous Gluconate in CVF at Non-
EVMS Sites for Subjects with Fewer Than 5 PMS per HPF in the
Cervical Mucus after Sex    | Ovaprene with at Least One PCT Cycle |
| 14.2.2.2-E           | Summary of the Levels of Ferrous Gluconate in Cervix at Study Site EVMS  | Ovaprene with at Least One PCT Cycle |
| 14.2.2.2-E-5PMS      | Summary of the Levels of Ferrous Gluconate in Cervix at Study Site EVMS for Subjects with Fewer Than 5 PMS per HPF in the Cervical Mucus after Sex       | Ovaprene with at Least One PCT Cycle |
| 14.2.2.2-NE          | Summary of the Levels of Ferrous Gluconate in Cervix at Non-EVMS Sites   | Ovaprene with at Least One PCT Cycle |
| 14.2.2.2-NE-
5PMS | Summary of the Levels of Ferrous Gluconate in Cervix at Non-
EVMS Sites for Subjects with Fewer Than 5 PMS per HPF in the
Cervical Mucus after Sex | Ovaprene with at Least One PCT Cycle |
| 14.2.2.3-E           | Summary of Cervical Mucus pH Values at Study Site EVMS   | Ovaprene with at Least One PCT Cycle |

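### Planned tables relate device position and dislodgement to the PCT only as <5 PMS or not, so a rise in count that stays below 5 per HPF would not appear in them

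*SAP*

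**What the plan says.** The protocol makes device location a fit endpoint (5d in the Synopsis and Section 6) and asks for the "relationship of position to PCT results, safety, and acceptability". For the primary objective, Section 6 describes PCT results in two ways: the proportion with fewer than 5 PMS per HPF, and the distribution of the average count over 9 HPFs.

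SAP 3.6 a) defines the <5 proportion at visit BP2, the baseline cycle without a device. Directly beneath it stands "This primary efficacy analysis will be repeated by subgroups for", followed by six subgroups. Number (5) begins "Device position at the time PCT: Over cervical os" and continues with two off-os categories. Number (6) is "Dislodgments (dislodgement reported in cycle before the PCT visit vs. no dislodgements reported in cycle before PCT".

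In SAP 4.2.1 the matching tables are 14.2.1.1-Dev, "Number and Percent of Subjects with an Average of Fewer Than 5 Progressively Motile Sperm per HPF in Cervical Mucus by Device Position", and 14.2.1.1-Dis, whose title ends "Progressively Motile Sperm per HPF in Cervical Mucus by Subjects Had Ring Dislodgement or Not". The count itself is in Table 14.2.1.2, "Average Number (across 9 HPFs) of Progressively Motile Sperm per HPF in Cervical Mucus and Change from Baseline Cycle to Ovaprene PCT Cycles", which is listed once, for the whole population. Protocol 14.2.6 also links position to the PCT through success alone.

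Two listings put counts next to displacement. SAP 3.9 h) lists subjects with clinician-assessed displacement and their PMS results in the cycle after it. SAP 3.6 a) flags PMS records that follow a diary-reported or clinician-noted dislodgement.

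**The concern.** The average count (MUAVPMS) is recorded as a number, and the SAP summarises it as one overall. For the position question the planned tables reduce it to pass or fail at 5. Protocol Section 4 expects fewer than 5 if the device works, and SAP 2.1 reports that the pilot saw no PMS in cervical mucus with the device in place. If most Ovaprene cycles pass, a displaced device that lets through 1 to 4 sperm per HPF falls in the same cell as a seated one that lets through none. The study could then report no relationship between position and PCT result when passage had in fact risen within the passing range.

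The placement of the subgroup sentence adds a second problem. Read literally, it asks for Ovaprene position and dislodgement at a visit where no device is worn.

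**Working it through.** The plan gives no power, alpha, effect size or expected success rate for this relationship, and no test, so there is no figure to reproduce. The check sets out which statistics reach the position comparison and then illustrates what is lost.

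**1. Statistics by position or dislodgement**

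| PCT statistic | Overall | By position | By dislodgement |
|---|---|---|---|
| Number and percent <5 | 14.2.1.1 | 14.2.1.1-Dev | 14.2.1.1-Dis |
| Average count and change from baseline | 14.2.1.2 | none listed | none listed |
| Individual counts | listings | displaced subjects only (3.9 h) | flag in listing (3.6 a) |

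**2. The <5 tables if every woman passes.** With the SAP's exact binomial interval, n passes out of n give a lower 95% limit of 0.025^(1/n):
- 20 of 20: 83.2% to 100%
- 5 of 5: 47.8% to 100%
- 3 of 3: 29.2% to 100%

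All rows read 100% and differ only in interval width.

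**3. How often that happens.** Only the figure of about 25 completers comes from the documents (SAP 2.5). The rest is assumed: one Ovaprene PCT per woman, 5 women displaced, woman-level gamma means with shape 0.5, Poisson counts over 9 HPFs, and a mean of 0.2 PMS per HPF when seated. There were 4,000 runs. Fisher's test on <5 and the Wilcoxon test on the count, both two-sided at 0.05, serve only as measures of information.

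| Displaced mean | Displaced pass rate | All 25 pass | Detected by <5 | Detected by count |
|---|---|---|---|---|
| 1 | 97.2% | 87% | 0.8% | 36% |
| 2 | 88.5% | 55% | 10.5% | 59% |
| 5 | 67.2% | 13% | 53% | 80% |
| 10 | 52.4% | 4% | 78% | 88% |

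As a check, seated women pass in essentially every run, so the all-pass chance should be close to the displaced pass rate to the fifth power. For a mean of 2, 0.885^5 = 0.54; for a mean of 10, 0.524^5 = 0.04. Both agree with the simulation.

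At a displaced mean of 2, detection by <5 against the count is 4% against 43% with 3 women displaced, and 6% against 69% with 8.

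**4. A model with larger effects.** A second assumed model shifts latent sperm passage by 1 SD when the device is off the os. It gives displaced failure rates of 14.6%, 22.6% and 34.3% when 2%, 4% and 8% of seated cycles fail. The chance that every displaced cycle passes is then:
- 10 displaced cycles, treated as independent: 0.854^10 = 0.21, 0.774^10 = 0.08, 0.657^10 = 0.015
- 5 displaced women: 0.854^5 = 0.45, 0.774^5 = 0.28, 0.657^5 = 0.12

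With 10 displaced cycles, at least one displaced failure would be visible in about 79% to 98% of trials.

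**The case against.** The strongest reply is that fewer than 5 PMS is the documents' own definition of an acceptable barrier. Appendix 2 of the protocol presumes a lower count insufficient for conception, and Protocol 14.2.6 itself relates position to success. On that view the SAP follows the protocol, and separating 0 from 1 to 4 is extra detail on a tertiary endpoint. This stands as a reason to keep the <5 tables and to rate the point low. It does not remove the gap, because the protocol's primary endpoints also describe the PCT by the count, and Protocol 14.2.2 bases qualitative change from baseline on the median and IQR.

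A reader might infer that counts are never set beside displacement, or that the tables cannot show a displacement effect at all. The documents support neither reading. The listing in SAP 3.9 h) and the flag in 3.6 a) give individual counts, and with few displaced cycles those can be read one by one. They lack a summary and a seated comparison, and 3.9 h) is not tied to position at the PCT. A large effect would usually show in the <5 tables, as step 4 and the last row of step 3 demonstrate.

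The SAP wording is also ambiguous. Section 3.6 introduces the primary efficacy analysis as the whole set of lettered endpoints, so the subgroup sentence could cover the numeric ones. The table list points the other way but is not conclusive: it has no table for subgroup (2), mode of delivery, and the table shells are a separate document that could not be checked. The title of Table 14.2.1.2 does not suggest position rows.

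Finally, no test is planned, so the detection rates measure information and are not properties of the design.

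**Conclusion.** The point holds as a minor one. No listed summary table describes the PMS count by device position or dislodgement, although relating position to PCT results is a stated endpoint and the count is in the dataset. An effect that takes counts to 5 or more would appear in the planned tables. A rise that stays below 5 would be visible only by reading listings.

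The size depends on assumptions about displacement frequency and the count distribution. With 5 of 25 women displaced and a tenfold higher mean (2 against 0.2), the <5 tables show no difference in 55% of simulated trials, and the count carries clearly more information (59% against 10.5% detection). At a displaced mean of 10 the gap is small (88% against 78%).

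That nearly every woman will pass is a fair inference from the pilot and from the conditional expectation in Protocol Section 4, but no rate is stated. Separately, bullet a) is the wrong anchor for subgroups (5) and (6), whatever the counts turn out to be.

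**What to change.** In SAP 3.6, attach subgroups (5) and (6) to bullets c) to g), the Ovaprene PCT endpoints, and state that they do not apply at BP2.

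Add two versions of Table 14.2.1.2, one by device position at the PCT and one by dislodgement before the PCT. Each should give n, mean, median, SD and IQR of MUAVPMS and of its change from BP2, at OP3A, at OP3B and over all Ovaprene cycles. Name the quartiles explicitly, because bullets d), e) and g) list only n, mean, median and SD. Many counts may be zero, in which case both medians can be 0, so also show the upper quartile and maximum, or the number with any PMS. Keep the <5 tables and the listings.

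A rank-based comparison of seated and displaced devices is optional. A Hodges-Lehmann shift says little when most counts are zero, and any interval on pooled cycles must allow for two cycles per woman.

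The data are already held in MUAVPMS, the Device Position CRF and the diary. The cost is a wording change and two more descriptive tables on small groups, which should be labelled as descriptive.

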An Ovaprene™ postcoital test (PCT) study in 21 women has been published.¹ Historically, the PCT was developed to evaluate couples with infertility, but it has been used in the initial evaluation of vaginal chemical and mechanical contraceptive barriers. In that setting, the PCT can demonstrate that, in the absence of the barrier, progressively motile sperm from the male partner can achieve access into the woman's midcycle cervical mucus, and, in the presence of the barrier, this access is reduced or eliminated. Three vaginal barrier devices, Lea's Shield, FemCap™, and the SILCS diaphragm (also known as Caya®), were evaluated by a postcoital study and then by a contraceptive effectiveness study prior to FDA approval. No progressively motile sperm were seen in midcycle mucus among all 10 users of Lea's Shield+Nonoxynol-9 (N-9) or in any of the 13 users of SILCS (Caya) diaphragm + N-9, and 6-month typical use pregnancy rates of 8.7% and 12.5% were observed in the subsequent contraceptive efficacy studies, respectively. Progressively motile sperm were seen in midcycle mucus in 1 of 7 users of FemCap+N-9 and a 6-month typical use pregnancy rate of 13.5% was observed in the contraceptive efficacy study. If PCT testing of Ovaprene™ were to show results similar to the results of these FDA-approved diaphragms, it is likely that Ovaprene™ would also show similar results in a contraceptive effectiveness study.

In the standard PCT test referenced above, the definition of a successful barrier function requires that thin cervical mucus is present during ovulation and that despite this, fewer than 5 progressively motile sperm per high power field (HPF) are seen in the cervical mucus. If the cervical mucus is thick, which may be the case if ovulation does not occur or if the test is done before or after ovulation, and there are fewer than 5 progressively motile sperm per HPF, the cycle must be repeated on the grounds that the thickness of the mucus may have prevented the appearance of sperm in it. Since Ovaprene™ is designed to release acid, which may increase cervical mucus viscosity, the interpretation of the PCT will require modification. The expected result, if Ovaprene™ is effective, will be fewer than 5 progressively motile sperm per high power field (HPF) in the cervical mucus, regardless of whether the mucus is thin or thick.

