#### 14.2.2 Sperm Penetration of Midcycle Cervical Mucus: Evaluation of Primary Objective

The primary method of evaluating changes in the PCT due to device use (primary objective) for each product condition will be the proportion of women and cycles (and 95% confidence interval [CI]) with an average (across 9 HPFs) of fewer than 5 PMS per HPF.

The mean, median, SD, and IQR of each woman's and cycle's average number (across 9 HPFs) of progressively motile sperm per HPF will be calculated separately for baseline and each test PCT. Qualitative assessments of change from baseline, if any, will be based on the median and IQR, because of expected non-normality of test cycle data. These descriptive statistics will be calculated by site and pooled across sites.

There will be no statistical comparison between Caya PCT cycle results and Ovaprene™ PCT cycle results. Caya PCT cycle results will be reviewed in the context of published Caya PCT studies; it is expected that Caya PCT results in this study will be similar to published Caya PCT results, which will give confidence to the Ovaprene™ PCT results in this study.

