# APPENDIX 2. ACTIONS AT THE PCT VISIT IN BASELINE AND TEST CYCLES (ADAPTED FROM SCHWARTZ ET AL, 2008)

		2008 /							
Vaginal pool - any sperm present (including	Mucus – adequate (thin)	Endocervix No sperm	Some sperm but an average of <5	An average of ≥5	Action at Baseline Cycle	Action at Test Cycle			
fragments) *			progressively motile/HPF**	progressively motile/HPF					
Yes	Yes	✓			Similar results in test				
Yes	Yes		✓		cycle would make it appear that the product	Barrier successful			
No	Yes		✓		was successful. Do not continue participant.	Continue to next cycle.			
Insufficient material	Yes		✓						
Yes	Yes			✓		Barrier failed.			
Yes	No			✓		If Caya cycle, do not continue participant if			
No	Yes			✓	Good PCT. Continue to	the result was clearly due to participant misuse of the product. Otherwise, continue to			
No	No			✓	next cycle				
Insufficient material	Yes			✓		next cycle. If Ovaprene ™ cycle, continue to next cycle.			
Insufficient material	No			✓		continue to next cycle.			
Yes	No	✓				If Caya cycle, repeat cycle.			
Yes	No		✓		Poor mucus may be responsible for scarcity or	If Ovaprene ™ cycle, continue to next cycle.			
No	No		✓		lack of sperm in cervix. Repeat cycle.	Considered successful for Ovaprene™ due to its			
Insufficient material	No		✓			potential mucus- thickening properties.			
No	Yes	✓							
No	No	✓			Ejaculation may not have taken place. Repeat cycle.	Ejaculation may not have taken place.			
Insufficient material	Yes	✓			taken place, kepeat cycle.	Repeat cycle.			
insufficient material	No	✓	:						

\* Absence of sperm in vagina means either that ejaculation did not take place or the vaginal environment is unusually hostile to sperm, possibly due to presence of spermicide in Caya cycle.

\*\* Confirms that ejaculation took place, but presumed to be insufficient for conception

Version: 06.00 (FINAL) Date: June 13, 2019

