- d) The sample size, mean, median, and standard deviation for the average number (across 9 HPFs) of progressively motile sperm per HPF in cervical mucus, across all treated subjects, in the presence of the Ovaprene® device. This is similar to that in Bullet b), but will be done at Visit OP3A, and also at Visit OP3B, by sub-setting the CRF MU data at VISIT\_ID = 14, and at VISIT\_ID = 19, respectively.
- e) The change from Baseline for the average number (across 9 HPFs) of progressively motile sperm per HPF in cervical mucus, across all Ovaprene® subjects. The change from Visit BP2 to Visit OP3A will be calculated by the value of MUAVPMS at Visit OP3A the value of MUAVPMS at Visit BP2. Then this change will be summarized by the sample size, mean, and median, and standard deviation across all treated subjects. Similarly, the changes from Visit BP2 to Visit OP3B will be calculated by replacing the Visit OP3A with OP3B.
- f) Overall percent of cycles with fewer than 5 PMS in the presence of Ovaprene® device. The numerator for this percentage will be the sum of all Ovaprene® device use cycles in the above Bullet c), and the denominator will be the total number of cycles from all treated with Ovaprene® and with MUAVPMS values.
- g) The sample size, mean, median, and standard deviation for the average number (across 9 HPFs) of progressively motile sperm per HPF in cervical mucus, across all Ovaprene® device cycles. This is similar to that in Bullet d), but will be inclusive of Visit OP3A and Visit OP3B.

Note that if a PCT cycle met the following 2 criteria that made the cycle invalid for the analysis, that cycle will be excluded from the efficacy analysis, but all safety data in that cycle will still be included in safety analysis:

- There is No, or Insufficient, material for sperm present in the vaginal pool, and
- Sperm at 100x and 400x also equals 'No'.

The secondary efficacy analysis will focus on the release of active component from the device in vaginal and cervix samples, and consists of the following endpoints:

- a) Determine the concentration release curve of ferrous gluconate in cervicovaginal fluid (CVF) over the first 4-6 hours after Ovaprene® insertion at one clinical site
- b) Determine whether the minimum target level of 8.2  $\mu$ g/mL is achieved in the first 4-6 hours after Ovaprene® insertion at one clinical site.

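### The SAP's invalid-cycle rule leaves out the inadequate-mucus rows of Protocol Appendix 2, so an uninterpretable Caya cycle can be counted as a barrier success

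*SAP*

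**What the plan says.** **SAP 3.6 (exclusion note).** The consequence is stated first: "if a PCT cycle met the following 2 criteria that made the cycle invalid for the analysis, that cycle will be excluded from the efficacy". The first condition is "There is No, or Insufficient, material for sperm present in the vaginal pool, and"; the second, which must hold as well, is "Sperm at 100x and 400x also equals 'No". Neither refers to mucus quality, and section 3.6 gives no other ground for excluding a cycle. Success is an average below 5.0 progressively motile sperm (PMS), with all women who have a PMS value at the visit as denominator. The efficacy analyses may be repeated for Caya, and SAP 4.2.1 lists Table 14.2.1.1-Ca for that purpose.

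**Protocol Appendix 2.** There are two separate reasons to repeat a cycle. One is that ejaculation may not have taken place. The other is inadequate mucus with no sperm or an average below 5, where the stated reason begins "Poor mucus may be responsible for scarcity or". For the second group a Baseline cycle is repeated, and the test-cycle column reads "If Caya cycle, repeat cycle". An Ovaprene cycle in the same rows is treated as successful. (Protocol 9.3.2 points to Appendix 3 for handling Caya results, but Appendix 3 holds fit criteria; the result rules are in Appendix 2.)

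**Protocol 4.** For the standard PCT with thick mucus and fewer than 5 PMS, "the cycle must be repeated on the grounds that the thickness of the mucus may have prevented the appearance of sperm in it". Only the Ovaprene interpretation is modified.

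**Protocol 14.2.2.** Caya results are expected to resemble published ones, "which will give confidence to the Ovaprene™ PCT results in this study".

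**The concern.** The protocol has already decided that a thick-mucus Caya cycle with few or no sperm says nothing about the barrier, because the mucus alone could explain the result. The SAP's rule keeps that cycle and scores it as a success.

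The Caya cycle is the study's positive control: it is there to show that these sites and couples reproduce what an approved barrier is known to do. Protocol 4 gives the benchmark: no progressively motile sperm in any of 13 users of this diaphragm with nonoxynol-9. Scoring uninterpretable cycles as successes can push the control only one way, toward that benchmark, and so weakens it as a check.

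Baseline is exposed in a similar but narrower way. A woman enters the analysis only after a successful baseline, so the risk there is that a superseded thick-mucus record is used in place of the valid repeat. It would then enter primary endpoints a), b) and e) as a low count without any device.

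**Working it through.** The plan states no figure on this point, and the sample size has no statistical basis (Protocol 14.1, SAP 2.5), so there is nothing to reproduce. The check has two parts.

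**1. Classify every Appendix 2 outcome under both rules, for a Caya cycle.** Inputs: vaginal pool (yes, no, insufficient), mucus (adequate, inadequate) and endocervix (no sperm, below 5, 5 or more), giving 3 × 2 × 3 = 18 combinations.

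| Group | Count | Appendix 2, Caya | SAP 3.6 |
|---|---|---|---|
| Endocervix 5 or more (3 × 2) | 6 | failure | failure |
| No endocervical sperm, pool no or insufficient (2 × 2) | 4 | repeat (ejaculation) | excluded |
| Inadequate mucus, remaining rows | 4 | repeat (mucus) | **success** |
| Adequate mucus, remaining rows | 4 | success | success |

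The sum is 6 + 4 + 4 + 4 = 18. The two rules disagree in one group only. Its four rows, all with inadequate mucus, are:

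- pool yes, no endocervical sperm;
- pool yes, below 5;
- pool no, below 5;
- pool insufficient, below 5.

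This assumes that an absence of sperm is recorded as an average of 0. If the field is left blank instead, the first row drops out and three remain.

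The SAP rule gives 8 success, 6 failure and 4 excluded. Adding the mucus criterion gives 4 success, 6 failure and 8 excluded (to be replaced by a repeat where there is one).

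**2. Size.** The documents give no frequency of inadequate mucus at the Caya PCT visit, so the number affected, k, is an assumption shown over a range. Take n = 25, the planned number of completers, with every first Caya result below 5. Intervals are exact binomial, as SAP 3.6 specifies: lower limit = Beta⁻¹(0.025; x, n − x + 1), upper limit = Beta⁻¹(0.975; x + 1, n − x). When x = n the lower limit is 0.025^(1/n); for n = 25 this is 0.025^0.04 = 0.863.

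| k | SAP as written | Excluded, no repeat done | Valid repeat used, all k fail |
|---|---|---|---|
| 1 | 25/25 (86.3–100%) | 24/24 (85.8–100%) | 24/25 = 96% (79.6–99.9%) |
| 3 | 25/25 (86.3–100%) | 22/22 (84.6–100%) | 22/25 = 88% (68.8–97.5%) |
| 5 | 25/25 (86.3–100%) | 20/20 (83.2–100%) | 20/25 = 80% (59.3–93.2%) |

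If the repeats succeed, the result stays at 25/25. Each affected woman therefore moves the Caya rate by at most 1/25 = 4 percentage points, and only if her valid repeat fails.

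**3. Ovaprene.** The same classification for an Ovaprene PCT cycle gives no disagreement. Appendix 2 itself counts the four inadequate-mucus rows as successful, and the four no-ejaculation rows are the ones that the SAP already excludes.

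**The case against.** **Thick mucus should be uncommon at the Caya PCT.** Under Protocol 9.3.2, Caya is dispensed only if the mucus score at CP1 is at least 10 and no sperm are found, and the PCT follows within 27 hours. Mucus would have to deteriorate within about a day. This stands, and it is why five affected women should be read as the far end of an illustration. It does not remove the case, since Appendix 2 still provides for it at the PCT visit.

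**Nothing formal hangs on the Caya proportion.** There is no statistical comparison with Ovaprene and no threshold, and the SAP text makes the Caya efficacy analysis optional. Tables 14.2.2.6-Ca and 14.2.2.7-Ca report Caya mucus scores, and all data are listed. This also stands in part: a careful reader could find the affected cycles. But the planned success table would still carry the wrong count.

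**A reader might infer that the primary Ovaprene proportions are inflated in the same way.** The documents do not support that. Thick-mucus Ovaprene cycles are successes by design, and the only PCT result that triggers an Ovaprene repeat is already excluded by SAP 3.6.

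**A reader might also infer that valid repeats will be lost.** SAP 3.6 selects Ovaprene data by fixed visit number ("but will be done at Visit OP3A, and at Visit OP3B"), and the only replacement rule for a repeated assessment, in SAP 3.7, covers safety data. But whether a repeat is filed under the same visit number depends on the case report forms and table shells, which are separate documents. If it is, selection by visit number retrieves it. For Ovaprene the residual risk is a missed valid repeat, not a false success.

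**Conclusion.** The point holds for the Caya positive control and, to a lesser degree, for Baseline. It goes beyond missing detail: SAP 3.6 states a validity rule, and that rule gives a different answer from the protocol in four of the 18 outcome combinations, always in the direction of success for Caya.

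The size is unknown and probably small. With 25 users assumed, the worst case runs from a 4-point fall (k = 1) to a 20-point fall (k = 5) in the Caya rate, and there is no change if the valid repeats succeed. The range rests on an assumed k and on all repeats failing; the documents support neither as an expectation. The Baseline effect further requires that a superseded record be the one analysed, which cannot be settled from the protocol and SAP.

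The Ovaprene success proportions are not altered by the missing mucus criterion. The correction should be made before analysis, so that no decision on which cycle counts is taken with results in view.

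**What to change.** Extend the exclusion note in SAP 3.6 along these lines: *For Baseline and Caya, a PCT cycle with mucus recorded as inadequate at the PCT visit and an average below 5 PMS per HPF, including no sperm, is invalid under Protocol Appendix 2 and is excluded. Where the cycle was repeated, the valid repeat is analysed in its place, once per woman. The numbers of excluded and repeated cycles are reported.*

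Appendix 2 gives no cutoff for inadequate mucus, and the score of at least 10 is applied at the mucus-check visit. The SAP should therefore name the recorded variable, and it should be the same case report form determination that sites use when they apply Appendix 2. The programming specification should state how repeat cycles are identified if they can be filed under another visit number; that also closes the residual Ovaprene risk.

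The cost is a few sentences and a small programming step, with no new data collection beyond what Appendix 2 already requires. The downside is a slightly smaller Caya denominator where no repeat was done.
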